Objectives:	
Primary Objectives:
 
 1. To assess the efficacy of –autoadjusting positive airway pressure (AUTOPAP) treatment in reducing 24-hour ambulatory blood pressure (ABP) in African American (AA) vs. - other (race) veterans with newly-diagnosed obstructive sleep apnea (OSA); 2. To assess the efficacy of –autoadjusting positive airway pressure (AUTOPAP) treatment in reducing central aortic blood pressure (CABP) in AA vs. other (race) veterans with newly-diagnosed obstructive sleep apnea (OSA); 3. To assess the efficacy of –autoadjusting positive airway pressure (AUTOPAP) treatment in reducing urinary biomarkers implicated in the pathogenesis of hypertension in OSA: 1) sympathetic nervous system activity (SNA; 24-hour urinary catecholamines) and 2) oxidative stress (overnight urinary 8-isoprostane) in AA vs. other (race) veterans with newly-diagnosed obstructive sleep apnea (OSA). 4. To test daytime dysfunction (excessive daytime sleepiness; EDS) as a moderator of reduction in ABP and CABP in AA and other (race) veterans following 3 months of AUTOPAP treatment. EDS will be measured objectively with psychomotor vigilance task (PVT) and subjectively with Epworth sleepiness scale (ESS). 
Secondary Objectives:
 
 5. To examine the association of reduction in ABP and CABP with genetic ancestry (using ancestry informative markers; AIMs in DNA), as genetic admixture is expected among self-identified ethnic groups (i.e., AA and other (race) veterans). 6. To analyze abnormalities in myocardial mechanics on transthoracic echocardiography (TTE) in obstructive sleep apnea and its reversibility with AUTOPAP treatment. 
Ancillary Objective:
 
 7. Tissue banking (whole blood processed for DNA, RNA, serum, and plasma) for future genomic studies.

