
Study Design (continued):
	
have any questions answered. Patients will be specifically consented for blood draw for tissue banking and for TTE and patients will be able to participate in the primary study without participating in the secondary and ancillary measures (blood draw for genetic testing, tissue banking, and TTE). Consenting patients will undergo preliminary eligibility assessments, including Berlin Sleep Questionnaire (BSQ), Epworth Sleepiness Score (ESS), Functional Outcomes of Sleep Questionnaire (FOSQ), medical history and physical examination, and CABP measurements. All eligible patients will perform a 10-minute psychomotor vigilance task (PVT). Specifically, consenting patients will have venous blood sampling (35 mL) for processing (DNA, RNA, serum, and plasma) and storage at UI Biorepository as well as a TTE scheduled at JBVAMC. A urine pregnancy test will be done for women of childbearing potential. All enrolled patients will initiate 7-day actigraphy with concurrent sleep logs (to estimate average nightly sleep duration), 24-hour urine collection, and 24-hour ABP recordings at completion of visit 1 and will be scheduled for an overnight portable monitoring (PM) test at Jesse Brown VAMC (Visit 2) or at home. If the PM test fails to record data due to technical or application errors, the patients may be asked to repeat this test once.
 
Visit #2: For patients performing home PM, visit 2 will be in the morning and PM device, actigraphy, sleep log, urine sample, and ABP monitor will be collected and processed/downloaded. Patients performing PM test at JBVA will arrive for the overnight PM. Actigraphy, sleep log, urine sample, and ABP monitor will be collected and processed/downloaded in the morning. All patients with apnea hypopnea index (AHI) \geq 15/hour on the PM test will be invited to continue.
 
AUTOPAPAUTOPAPAUTOPAPAUTOPAPRATIONALE ** We have eliminated polysomnography (VISIT 3) at Hines for two reasons:
 
 1. We noted refusals to participate in this project in the past year (45/190 Veterans approached) due to burden of traveling to Hines. To improve recruitment for this study and to meet target enrollment (n = 220) over next two years, we have therefore eliminated the requirement for polysomnography. The PM test will be used to diagnose patients with moderate to severe OSA; as is done in clinical practice and many research studies. 2. The primary goal of performing polysomnography was to obtain gold-standard diagnostic and electroencephalography data from polysomnography. However, we have noted suboptimal data quality from the 16 polysomnographies completed at Hines thus far. Substantial scientific advantage is not conferred to this project and its objectives with these polysomnographies. 
Visit #3: Patients will return to the clinic for AUTOPAP treatment set-up and education. AUTOPAP treatment adherence will be optimized with follow-up telephone contacts as specified in full protocol below.
 
Visit #4: Patients will return to clinic for repeat PVT, FOSQ, ESS, CABP measurements and to initiate 24-hour ABP and urine collection. Patients will also be scheduled for repeat TTE and blood draw for tissue banking
 
Final Visit # 5: Patients will return to clinic in the morning after initiating 24-hour ABP and urine collection, which will be collected and processed/downloaded. Patients

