2.2 Secondary Objectives

Studies in EA suggest the presence of excessive daytime sleepiness (EDS; symptom of OSA) is associated with a more robust hypertension response to AUTOPAP treatment. Our preliminary data indicate a higher prevalence of objective EDS in AA with OSA compared to EA after adjusting for socio-demographic factors. Thus, we will examine EDS as a moderator of hypertension response to AUTOPAP treatment and identify EDS by the Psychomotor Vigilance Test; PVT (higher number of lapses per trial is objective EDS) and ESS questionnaire.

There is significant genetic admixture among self-identified ethnic groups which introduces biological heterogeneity and potential confounding. We will identify genetic ancestry by known and specific DNA sequence variation(s), called Ancestry Informative Markers (AIMs) and explore the role of genetic (i.e. biologic) ancestry as a moderator of ABP and CABP outcomes.

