7.3 Withdrawal from Study Treatment Due to Adverse Experience

Patients withdrawn from receiving additional study drug due to an AE will be followed by the PI until resolution or stabilization of the event. Additional reports will be provided to the regulatory authorities when requested. Every effort will be made to follow the patient for the full study period as per the schedule of study visits.

8. Final Outcomes Assessment:

Table. Outcomes and covariates
Outcomes
Specific Aim 1. Between Group Comparisons (African Americans vs. Other): Measure change from pre-treatment to 3 months after AUTOPAP treatment: (a) Primary - average 24-hour systolic and diastolic BP (b) Secondary - central aortic blood pressure ii. average of 24-hour mean BP = diastolic + 1/3x (systolic - diastolic) iii. 24-hour urine norepinephrine & normetanephrine iv. Overnight urine 8-isoprostane levels
Specific Aim 2. (change from pre-treatment to 3 months after AUTOPAP treatment): (a) Primary (between-group comparison) - change in number of PVT lapses (b) Secondary (within-group comparisons) - i. Association of change in PVT lapses with primary outcome of specific aim 1. ii. Association of change in PVT lapses with secondary outcomes of specific aim 1. iii. Association of change in ESS scores with outcomes of specific aim 1.
Exploratory Aim 3. i. Within-group analysis of change in specific aim 1. primary and secondary outcomes (i. and ii.) with addition of Individual Ancestry as a covariate. ii. Velocity Vector Imaging (VVI) from echocardiography correlation with AHI. iii. Generate effect size estimates for AUTOPAP treatment on VVI.
Covariates: Specific Aims 1 and 2
Socio-demographic Characteristics 
 • Age (continuous) • Daily sleep duration on actigraphy (continuous) • Gender (categorical, 2 levels) • Education (categorical, 2 levels; ≤ high school, > high school) • Income per annum (categorical, 5 levels; <30K, 30-50K, 51-75K, 76-100K, >100K) • Smoking status (pack-years; continuous) • Alcohol use (number of drinks/week; continuous)
OSA Disease Severity 
 • AHI • Time below 90% oxygen saturation (T<90)
Co-morbid Medical Conditions 
 • Obesity: Body Mass Index (BMI) • General Health Status: Charlson Comorbidity Index (CCI)

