9.4 Statistical Analyses

9.4.1 Power and Sample Size Estimation: The primary goal of this initial study is to estimate differences in the effect size of AUTOPAP treatment on ABP and CABP in AA and EA's with moderate to severe OSA. Our preliminary data shows a reduction in office BP 3 months after AUTOPAP treatment and the effect size difference between-groups (by ethnicity; using differences in mean \pm SD change of BP and t-tests in PASS program, <http://www.ncss.com/pass.html>) was 0.42 for systolic and 0.53 for diastolic blood pressure. We determined that 99 patients in each group (total n = 198) will provide power of 0.8 in two-tailed tests with an alpha of 0.05 to observe a difference in effect size between groups of 0.4. Based on our prior experience we anticipate an attrition rate of 10-20%. Therefore, a total of 220 (198/0.90) patients enrolled will achieve the target of 198 patients completing the study. Our preliminary study of PM in our clinical population (selected with a positive BSQ) shows approximately 95% sensitivity and specificity of PM determined AHI of ≥ 15 /hour in terms of predicting PSG-determined AHI of ≥ 15 /hour (inclusion criteria). Therefore, we expect to screen approximately 260 patients (220/0.95).

9.4.2 Data analysis: A p-value < 0.05 will be considered significant. All variables and analysis goals are listed in table above. **Specific Aim 1.** Within group changes in primary and secondary outcomes will be assessed with repeated measures ANOVA implemented with PROC MIXED in SAS. A two-sample t-test (PROC TTEST in SAS) will be used to examine between-group differences in the treatment-related changes in primary and secondary outcomes. **Specific Aim 2.** Primary outcome will be assessed with a two-sample t-test (PROC TTEST in SAS). Secondary outcomes will be assessed with partial correlations implemented with PROC CORR in SAS.

Exploratory Aims 3. Effect of Individual Ancestry on changes in primary and secondary outcomes of specific aim 1 within group will be assessed with ANCOVA implemented with PROC GLM in SAS. Correlations (of VVI with AHI and change in VVI with change in AHI) will be assessed within groups.

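### The plan names only within-race ancestry ANCOVAs, so no named analysis shows whether ancestry alters the race difference or whether its slope differs by race

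*Combined protocol and SAP*

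**What the plan says.** Section 2.2 gives two reasons for measuring ancestry. One is confounding: "There is significant genetic admixture among self-identified ethnic groups which introduces biological heterogeneity and potential confounding". The other is moderation, since the same paragraph proposes to explore ancestry as a moderator of the ambulatory (ABP) and central aortic (CABP) outcomes. Synopsis objective 5 is "To examine the association of reduction in ABP and CABP with genetic ancestry". Neither that objective nor exploratory endpoint 7 in the synopsis is limited to analysis within a group.

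The analysis sections are narrower. Section 9.4.2 (Exploratory Aims 3) states: "Effect of Individual Ancestry on changes in primary and secondary outcomes of specific aim 1 within group will be assessed with ANCOVA", using PROC GLM. The outcome table in Section 8 repeats a within-group analysis "with addition of Individual Ancestry as a covariate". The only named between-race test of the Aim 1 outcomes is a two-sample t-test. Every test is judged at p < 0.05.

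The Moderators paragraph of Section 9.4 describes a linear model with Z and Z*X, using gender as its example. It names neither ancestry nor race. The genetic blood draw is optional (synopsis, Study Design; Section 3), so fewer patients may have ancestry data than complete the study.

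**The concern.** Confounding and moderation are questions about race and ancestry together. Whether the AA versus Other difference shrinks or grows when ancestry is held fixed can be seen only in a model with both terms. Whether ancestry acts differently in the two groups needs a comparison of slopes. Two separate ANCOVAs give two slopes and two p-values, but neither of these results.

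If the analysis stops there, the available comparison is that one p-value is below 0.05 and the other is not. That is a poor guide to whether slopes differ, because it depends heavily on how much ancestry varies within each group.

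**Working it through.** **Inputs from the documents (Section 9.4):** two-sided alpha 0.05, standardised difference 0.4, power 0.80, 99 completers per group, and p < 0.05 for each test.

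**Inputs assumed, because the documents do not give them:** 99 genotyped per group (the most that the completer target allows), the same true slope and residual SD in both groups, and power of the AA slope test (80%, with 50% as an alternative). The ratio r = ancestry SD in Other / ancestry SD in AA is varied from 0.17 to 2.

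**1. The plan's own figure.** The plan states: "99 patients in each group (total n = 198) will provide power of 0.8 in two-tailed tests with an alpha of 0.05". The standardised difference behind this is 0.4. Check: 2 x (1.960 + 0.842)^2 / 0.4^2 = 98.1, rounded up to 99. Enrolment is 198 / 0.90 = 220. Both reproduce. They concern the between-race comparison; no power is stated for ancestry.

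**2. Are the within-group slopes confounded by race?** No. In 4,000 simulated trials with a pure race effect of 0.4 SD and no ancestry effect, the slopes averaged 0.002 and -0.002. They were significant in 4.5% and 4.9% of trials.

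**3. Comparing two p-values when the true slopes are equal.** The standard error (SE) of a within-group slope is sigma / (ancestry SD x sqrt(n)). With 80% power in AA, the noncentrality is 2.802 in AA and 2.802r in Other. Power in Other = Phi(2.802r - 1.960) + Phi(-2.802r - 1.960). The groups are independent, so:

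- P(AA only) = 0.80 x (1 - power in Other)
- P(Other only) = 0.20 x power in Other

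| r | Power in Other | AA only | Other only | Exactly one |
|---|---|---|---|---|
| 0.17 | 0.075 | 0.740 | 0.015 | 0.755 |
| 0.25 | 0.108 | 0.714 | 0.022 | 0.735 |
| 0.5 | 0.288 | 0.569 | 0.058 | 0.627 |
| 0.75 | 0.556 | 0.355 | 0.111 | 0.466 |
| 1 | 0.800 | 0.160 | 0.160 | 0.320 |
| 1.5 | 0.988 | 0.010 | 0.198 | 0.207 |
| 2 | 1.000 | 0.000 | 0.200 | 0.200 |

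(Small differences in sums are rounding.) With 50% power in AA, exactly one test is significant in 50% of trials at every r, since 0.5(1 - p) + 0.5p = 0.5. With no ancestry effect in either group the figure is 2 x 0.05 x 0.95 = 9.5%. With 60 genotyped per group and the same AA power, the pattern is unchanged.

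**4. Interaction test.** In simulations of the joint model with equal true slopes, race x ancestry was falsely significant in about 4-6% of trials.

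**5. Race effect adjusted for ancestry.** Assume mean ancestry 0.80 and 0.15 and SD 0.12 in each group. In units of the residual SD, the variance of the race coefficient is 2/99 + 0.65^2 / [99 x (0.12^2 + 0.12^2)] = 0.0202 + 0.1482 = 0.1684, so the SE is 0.41. The simulation gave 0.43, because holding ancestry between 0 and 1 narrows its spread. Without ancestry the SE is sqrt(2/99) = 0.14. Simulated power for a race effect of 0.4 SD, adjusted for ancestry, is 15%.

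**6. Common slope.** With equal slopes and residual variances, the noncentrality of the common slope is 2.802 x sqrt(1 + r^2). Its power is about 0.83, 0.88, 0.94 and 0.98 for r = 0.25, 0.5, 0.75 and 1. The gain is not guaranteed. Let k be the Other/AA ratio of ancestry sums of squares and L the Other/AA ratio of residual variances. The variance of the ordinary pooled slope, relative to AA alone, is (1 + kL) / (1 + k)^2, which exceeds 1 when L > 2 + k.

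**The case against.** A reader might infer that the plan cannot separate ancestry from race at all. The documents do not support that. A slope fitted inside one self-identified group holds race fixed, as step 2 shows, and objective 5, read as asking for an association, is answered by such slopes.

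A reader might also infer that the trial will tend to report an ancestry effect in AA only. That needs two things the documents lack. One is a rule that significance in one group is read as an effect specific to it. The other is an ancestry spread narrower in Other than in AA. Other now means any non-AA race (synopsis, Eligibility; Section 4.1), so the spread could be wider there; at r = 1.5 or more, one-group significance falls almost entirely on Other.

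The best defence of the plan is that Section 2.2 calls ancestry a moderator and the Moderators paragraph prescribes an interaction model. Taking Z as ancestry and X as race gives the missing test. That is a possible reading, but nothing makes the link, and the sentence that does name ancestry assigns it a within-group model.

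Two further points stand. Making a pooled common slope the main analysis would be partly a preference, since it needs similar slopes and residual variances, and Other may be heterogeneous. And adding ancestry to a race model will not settle the confounding question, given the precision in step 5.

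**Conclusion.** The concern holds in a limited form. The named ancestry analyses are valid within each group, but they provide neither an ancestry-adjusted race difference nor a comparison of slopes, and Section 2.2 gives the plan's own reasons for wanting both. The general moderator model could fill part of the gap but is not assigned to ancestry.

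If separate p-values were used to compare the groups, exactly one would be significant in about 20-75% of trials with identical slopes, against about 5% false positives for an interaction test. The range rests on the assumed 80% power in AA and on r between 0.17 and 2; a weaker ancestry effect can give a lower figure, down to 9.5% when there is none. The direction cannot be predicted from the documents.

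The consequence is modest. The aim carries no power claim and is labelled exploratory in the synopsis endpoints, Section 8 and Section 9.4.2, although the synopsis objectives list it as secondary.

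**What to change.** In Section 9.4.2 (Exploratory Aims 3), keep the within-group ANCOVAs and add, for each outcome on all genotyped patients, a PROC GLM with race + ancestry and the listed covariates, followed by race x ancestry. The covariate list in Section 8 is headed for Aims 1 and 2, so say that it applies here. State that the Moderators paragraph covers ancestry.

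Report with confidence intervals:

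- the difference between the two ancestry slopes;
- the race coefficient with and without ancestry, on the same genotyped patients.

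Report a common slope only if slopes and residual variances look similar, or use robust standard errors. State that a group-specific effect will not be inferred from separate p-values. If the three-population ancestry model in Appendix III is chosen, enter two ancestry components.

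The cost is one added model statement per outcome, on data already planned. The main downside is collinearity: the adjusted race effect has an SE of about 0.43 SD under the assumptions in step 5, so it should be read by its interval. The slope difference is also less precise than either slope alone, so a non-significant interaction is not evidence that the slopes are equal.

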Exploratory Endpoints:	
 7. Test association of genetic ancestry with endpoints 1 to 3. 8. Test association of myocardial mechanical data from TTE with AHI (OSA severity). 9. Generate effect size estimates for change in myocardial mechanics with 3 months of AUTOPAP treatment.
-------------------------------	---

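### The exploratory VVI–AHI correlation is planned only within each race group, with no covariates and no overall estimate, although the question it serves is not about race

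*Combined protocol and SAP*

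**What the plan says.** Section 9.4.2, under Exploratory Aims 3, gives the whole analysis of the echocardiographic association in one sentence: "Correlations (of VVI with AHI and change in VVI with change in AHI) will be assessed within groups". The Study Design section of the synopsis defines two groups, African American and other-race veterans, with 110 planned in each.

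The statements of the question do not mention race:

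- Synopsis, Objectives, item 6: "To analyze abnormalities in myocardial mechanics on transthoracic echocardiography (TTE) in obstructive sleep apnea and its reversibility with AUTOPAP treatment".
- Synopsis, Exploratory Endpoints, item 8: "Test association of myocardial mechanical data from TTE with AHI (OSA severity").
- Section 8 outcomes table, Exploratory Aim 3, item ii: "Velocity Vector Imaging (VVI) from echocardiography correlation with AHI".
- Section 2.2 motivates the work by the effect of OSA severity and treatment on subclinical cardiac function, again without a race contrast.

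In that table the within-group label belongs to item i, the ancestry analysis: "Within-group analysis of change in specific aim 1. primary and secondary outcomes".

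The covariate part of the table is headed "Covariates: Specific Aims 1 and 2". Age, gender and BMI appear under that heading. For Aim 2, Section 9.4.2 names an adjusted method: "Secondary outcomes will be assessed with partial correlations implemented with PROC CORR in SAS". For VVI it says only correlations.

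**The concern.** The analysis does not match its question. Section 2.2 says that earlier findings on myocardial deformation and OSA severity have been inconsistent. The useful contribution here would be one reasonably precise, adjusted estimate. Followed literally, the plan gives two less precise crude ones.

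Three things follow.

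1. **Precision.** Each correlation uses about half of the patients with an echocardiogram.
2. **Interpretation.** With two separate tests and no test of their difference, significance in one group only is easily read as a race difference.
3. **Confounding.** BMI and age may plausibly relate both to AHI and to myocardial deformation. If they are not controlled, a correlation between VVI and AHI need not reflect OSA severity. Both are already collected.

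**Working it through.** **The plan's own figure.** No sample size is stated for this correlation. The only stated size is for the between-group blood pressure comparison, and it reproduces. With a standardised difference of 0.4, two-sided alpha 0.05 and power 0.80, n per group = 2 × (1.960 + 0.842)² / 0.4² = 98.1, rounded up to 99. The total is 198, and 198/0.90 = 220 enrolled.

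**Which n applies.** VVI against AHI is a baseline association, so it does not need 3-month completers. The relevant maximum is the enrolled number: 110 per group, 220 overall.

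**Precision (Fisher z).** With k covariates partialled out:

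- detectable r at 80% power = tanh[(1.960 + 0.842)/√(n − 3 − k)]
- power = Φ[atanh(r) × √(n − 3 − k) − 1.960]

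The overall figures use k = 3 for illustration. Uptake of the optional echocardiogram is not given, so the rows below 100% are assumptions.

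| Uptake | Per group, k = 0 | Overall, k = 3 |
|---|---|---|
| 100% | n = 110, r = 0.264 | n = 220, r = 0.189 |
| 50% (assumed) | n = 55, r = 0.370 | n = 110, r = 0.268 |
| 25% (assumed) | n = 28, r = 0.508 | n = 56, r = 0.377 |

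For the first row: 2.802/√107 = 0.271 and tanh gives 0.264; 2.802/√214 = 0.192 and tanh gives 0.189. With four covariates, as in the fix below, 2.802/√213 gives 0.190, so the choice of k hardly matters.

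Power for a true r of 0.20 (atanh = 0.2027) at full uptake:

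- per group: Φ(0.2027 × 10.344 − 1.960) = Φ(0.137) = 0.55
- overall: Φ(0.2027 × 14.629 − 1.960) = Φ(1.006) = 0.84

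Near r = 0 the 95% half-width is tanh(1.960/√107) = 0.187 per group and tanh(1.960/√217) = 0.132 in all patients without covariates, a ratio of about 1.4.

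**Two tests.** Two independent tests at 0.05 give a 1 − 0.95² = 9.75% chance of at least one false positive.

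**Confounding by BMI (illustration).** Suppose AHI and VVI are unrelated once BMI is fixed. The crude correlation is then r(AHI,BMI) × r(VVI,BMI). The documents give neither value. Assuming 0.2 to 0.5 for the first and 0.2 to 0.4 for the second, the spurious correlation runs from 0.2 × 0.2 = 0.04 to 0.5 × 0.4 = 0.20. At n = 110 the two-sided rejection rate is:

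- lower end: Φ(0.414 − 1.960) + Φ(−0.414 − 1.960) = 0.061 + 0.009 = 0.07
- upper end: 0.55 (the same calculation as the per-group power above)

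The nominal rate is 0.05.

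**The case against.** The strongest reply has four parts.

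*Nothing is lost.* A reader might infer that the plan throws away half the sample. It does not: both groups are analysed. Combining the two within-group Fisher z values uses (110 − 3) + (110 − 3) = 214, which gives a detectable r of 0.189, the same as the overall partial correlation. Within-group analysis also removes confounding by race, so a plain pooled correlation that ignored race would be no improvement. All of this stands. What is missing is any instruction to combine.

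*The gaps are inferred from silence.* Nowhere is this analysis called unadjusted. Section 9.4.2 also points to the outcomes table for its analysis goals, and item ii there carries no within-group restriction. That is fair, and at the least table and text need to be aligned. But the text names the within-group form explicitly, the covariate heading excludes Aim 3, and partial correlations are named only for Aim 2. Two crude correlations are the natural reading. The missing-data paragraph of Section 9.4.2 adds covariates related to missingness, which is a different purpose.

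*Blood pressure is not clearly a confounder.* It is tempting to list it beside BMI. Section 1 opens by presenting hypertension as a consequence of OSA, so blood pressure may lie on the path from AHI to myocardial mechanics. Forcing it into the main model would change the question. This stands.

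*The tool for a race difference is already in the plan.* The moderator paragraph of Section 9.4.2 describes the interaction method. True, but it is not tied to this analysis.

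A reader might also extend the point to the within-group associations of Aim 2. The documents do not support that. Synopsis objective 4 names both race groups, the outcomes table labels those associations within-group on purpose, and partial correlations are already specified for them.

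**Conclusion.** The concern holds as a mismatch between question and analysis, and as an absent adjustment set. It is not a loss of patients. At full baseline uptake the detectable correlation is 0.264 per group against 0.189 overall, and power for r = 0.20 is 0.55 against 0.84. These figures assume that all 220 enrolled patients have a usable echocardiogram, which is the most favourable case. Any lower uptake worsens both sides, and the split remains the less precise option. The BMI figures are illustrative, because they rest on assumed correlations; age is a plausible confounder that was not quantified.

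The weight is modest. The aim is exploratory, the study was not sized for it, and the primary blood pressure comparison is untouched. The change is still worth making, because it uses data already collected and keeps the race-specific results.

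**What to change.** In Section 9.4.2, for VVI with AHI, replace the within-group wording with the following, and align item ii of Exploratory Aim 3 in the outcomes table:

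1. **Main analysis:** one partial correlation, or one regression of VVI on AHI, in all patients with a baseline echocardiogram, adjusted for self-identified race, age, sex and BMI.
2. **Sensitivity analysis only:** the same model with 24-hour systolic pressure added, noting that it may be on the pathway from OSA.
3. **Group difference:** a race-by-AHI interaction in a separate model, using the plan's moderator method. If it sits in the main model with race coded 0/1, the AHI coefficient becomes the slope in the group coded 0 and is no longer an overall estimate.
4. **Within-group correlations:** reported descriptively with intervals.

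Extend the covariate heading in Section 8, or add a line for Exploratory Aim 3, so that the adjustment set is stated in advance.

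The cost is plan wording, slightly more analysis work and a few degrees of freedom. No new data are needed.

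This change does not cover the second half of the sentence. Change in AHI needs a post-treatment AHI, and neither the Section 3 description of Visits 4 and 5 nor Appendix I schedules a repeat portable monitoring test. Its source should be defined separately.

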Study Design:	
This is an interventional parallel group (AA and other (race) veterans) efficacy study of AUTOPAP (standard first- line) treatment in 220 veterans with OSA. Patients will be enrolled consecutively to reach target enrollment of 110 in each group. All outcomes assessment will be done 3 months after AUTOPAP treatment initiation.
 
Recruitment Site: Sleep, Tele-sleep (for Adam Benjamin Jr CBOC), Pulmonary, and Primary Care Clinics at JBVAMC. In addition, local IRB approved study flyers will be posted in sleep and pulmonary clinics at Hines and North Chicago VA.
 
Initial Screening Visit #1: At the first clinic visit, each patient will be provided with oral and written information (informed consent form) describing the study and will

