Residuals and outliers: Linear models require residuals from model fits to follow a normal distribution and be free of outliers. We will examine residual distributions and apply transformations to outcomes and explanatory variables as warranted to achieve normality. Further model checks will employ partial regression plots; outliers will be dealt through case removal, influence down-weighting (robust M-estimation), or bootstrapping of estimators. Missing data: We will examine patterns of missingness with respect to covariates and include any covariates differentially associated with missing data. Correctly specified linear mixed models yield unbiased estimates for data missing at random (MAR); multiple imputation can also be employed. It is possible that subjects' treatment experiences will affect missingness (dropout), in which case data is not missing at random (NMAR) or nonignorable, and requires additional modeling, such as pattern-mixture models.

Moderators: Whether a moderator variable Z affects the association of explanatory variable X and outcome Y will be examined by introducing Z and the $Z*X$ interaction in the linear model. When Z is a (0,1)-indicator variable (e.g., gender), the coefficient for Z is the adjustment to the intercept and the coefficient for $Z*X$ is the adjustment to the slope appropriate for the group coded 1; the latter coefficient tests the moderator effect.

Mediators: None hypothesized.

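### Section 9.4.2 lets the analyst delete patients, change method or transform outcomes after seeing residuals, with no rule fixed in advance; this can inflate the 5% error rate of the race comparison

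*Combined protocol and SAP*

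**What the plan says.** The outcome table in Section 8 gives the primary outcome of Specific Aim 1 as change in "average 24-hour systolic and diastolic BP", compared between African American and other veterans. Section 9.4.2 names the test: "A two-sample t-test (PROC TTEST in SAS) will be used to examine between-group differences in the treatment-related changes in primary and secondary outcomes". The threshold is "A p-value < 0.05 will be considered significant".

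The residuals and outliers paragraph of the same section says that residuals will be inspected and that outcomes and explanatory variables may be transformed towards normality. It adds that "outliers will be dealt through case removal, influence down-weighting (robust M-estimation), or bootstrapping of estimators". It does not define an outlier, rank the three options, say who chooses or when, mask the chooser to race, or require the result in all patients to be reported.

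The nearest safeguard is Section 9.3. Implausible values found in descriptive statistics are resolved before analysis, the dataset sent to the analysis core carries no identifiers, and scripts are documented and kept.

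**The concern.** A test has its nominal error rate only if the data set and the method are settled without reference to the result. Here three things stay open until residuals are on the screen: which patients are in, which estimator is used, and on which scale.

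Deletion raises a further problem. A residual is a deviation from a fitted value, and in a two-group comparison the fitted value is the group's own mean. Cutting both groups back around their own means reduces the estimated variance, but the difference between the means does not become correspondingly more precise. The test then rejects too often even if one cut-off is applied mechanically.

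At stake is the main claim of the study, that African American veterans respond more to treatment. Unusually large and unusually small responses bear directly on that claim. Race is not randomised and no masking is described, so exclusions chosen late would be hard to defend.

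**Working it through.** **Inputs from the documents.** Two-sided alpha 0.05, power 0.80, standardised difference 0.4 and 99 completers per group (Section 9.4.1); 110 enrolled per group (Study Design synopsis); two-sample t-test (Section 9.4.2). **Assumed, because the documents are silent:** the cut-off (2, 2.5 or 3 SD) and the distribution of BP change.

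**1. The plan's own figure.** n = 2(1.96 + 0.8416)²/0.4² = 2 × 7.849/0.16 = 98.1, so 99 per group. Power at 99 is Φ(0.4·√(99/2) − 1.96) = Φ(0.854) = 0.80. Enrolment is 198/0.90 = 220. The sample size reproduces and is not in question here.

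**2. Deletion on residuals from each group's own mean, normal data.** For cut-off c, let P = 2Φ(c) − 1 be the share kept, d = 2cφ(c)/P, and V = 1 − d the variance of the kept values. Per group and per patient enrolled in the analysis:

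- variance the t-test estimates for the trimmed mean: V/P
- actual variance: V/P + 2dV + d²

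The extra terms arise because the retention window moves with the group's own mean. A group that is high by chance keeps more of its high values. The rejection rate is about 2[1 − Φ(1.96·r)], with r = √(estimated/actual).

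| c | P | d | V | estimated | actual | r | 1.96·r | type I error | deleted of 198 under normality |
|---|---|---|---|---|---|---|---|---|---|
| 2 | 0.9545 | 0.2263 | 0.7737 | 0.8106 | 1.2119 | 0.8178 | 1.603 | 10.9% | 9.0 |
| 2.5 | 0.9876 | 0.0887 | 0.9113 | 0.9227 | 1.0923 | 0.9191 | 1.801 | 7.2% | 2.5 |
| 3 | 0.9973 | 0.0267 | 0.9733 | 0.9760 | 1.0286 | 0.9741 | 1.909 | 5.6% | 0.5 |

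**3. Deletion on the pooled distribution, blind to group.** The window is common to both groups, so its movement cancels from the difference. The terms in d vanish, estimated equals actual, and the rate stays at 5%.

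**4. Simulation.** 20,000 to 40,000 null trials per setting, 99 per group. Four assumed distributions: normal; normal with 5% of values at three times the SD; t with 5 df; t with 3 df. Ranges are across the four.

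| Procedure | 2 SD | 2.5 SD | 3 SD |
|---|---|---|---|
| Own-group residuals, fixed cut-off | 7.8-11.0% | 6.3-7.3% | 5.4-6.1% |
| Full or own-group trimmed test, whichever is significant | 10.1-11.7% | 7.8-8.8% | 5.8-8.0% |
| Pooled deletion, fixed cut-off | 4.8-5.0% | 4.9-5.1% | 4.9-5.1% |
| Full or pooled-trimmed test, whichever is significant | 7.4-7.9% | 6.4-7.7% | 5.5-7.3% |

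For comparison, the t-test on all patients gave 4.7-5.3%, and Huber M-estimation fixed in advance gave 5.1-5.4%. The last row shows that even group-blind deletion protects the error rate only if it is the sole analysis. Transformations were not simulated; they add further choice.

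**The case against.** Much of the case on the other side stands.

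- **Deletion is not mandatory.** The three options are joined by *or*, and being listed first gives deletion no priority. A reader might infer that the clause does inflate the error rate and that the primary p-value is invalid. The documents do not support that: an analyst who fixed Huber estimation, or group-blind deletion, before looking would stay near 5%.
- **The size rests on assumptions.** The plan states no cut-off. A 2 SD rule would remove about 9 of 198 patients from clean normal data, which few analysts would do. At 3 SD the excess is under one point on normal data, and at 3.5 or 4 SD it is essentially nil (5.2% and 5.1%).
- **Selecting by result is not described.** A reader might quote the 12-13% found when the full t-test, all three deletion cut-offs, Huber and bootstrap are all tried and any success counts. Nothing in the plan says the analyst will work that way. Analysis by a separate core with preserved scripts makes choices traceable, though it does not fix them beforehand, and removing identifiers does not hide race.
- **Scope is inferred.** The paragraph speaks of linear models and partial regression plots, which suits the covariate models better than a t-test. But a two-sample t-test is a one-factor linear model, and the text exempts nothing.
- **Flagged values may not be genuine.** It is tempting to say that, after the cleaning in Section 9.3, every remaining extreme is a true response. That is unproven: an ambulatory recording counts as valid with 70% of expected readings, so artefact could survive.

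What remains is that the method behind a p-value judged at 0.05 is left to a choice made after residuals are seen.

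**Conclusion.** The concern holds as a gap in pre-specification that can inflate the type I error of the between-group comparison. It does not hold as a demonstration that the error rate will be inflated.

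Under a fixed cut-off on own-group residuals and normal data, the nominal 5% becomes about 11%, 7% or 5.7% at 2, 2.5 or 3 SD. If either the full or the trimmed test may carry the claim, the range is about 6-12% across cut-offs and distributions. All of this assumes 99 per group, no true difference, and deletion relative to each group's own mean. That is the natural reading of model residuals, but the plan does not spell it out for the t-test. With group-blind deletion or one robust method, settled in advance and used alone, the rate stays near 5%.

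Confidence is high that the rule is missing and low on the size of the effect in this trial. The sample size of 99 per group is unaffected. The point should be corrected before the data are analysed.

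**What to change.** Replace the outlier sentence and the open-ended transformation sentence in Section 9.4.2 with wording to this effect:

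1. The primary between-group analysis is the two-sample t-test on untransformed change from baseline, using all valid recordings.
2. Only documented recording errors, handled under Section 9.3, are excluded. That decision is made and recorded without sight of race group.
3. No patient is removed because of a residual.
4. One named robust analysis, Huber M-estimation with its tuning constant stated, is reported beside the primary result as a sensitivity analysis. Any transformed analysis has the same status. Neither can replace the primary result.

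The cost is a few sentences and one extra run, with no change to sample size or study procedures. The downside is a slightly wider confidence interval if BP changes turn out heavy-tailed; the Huber analysis would show whether that matters.
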